#### 1.4 Rationale

This study is designed to determine if adding durvalumab both during and after thoracic radiation for locally advanced NSCLC provides comparable outcomes to concurrent chemoradiation followed by consolidation durvalumab. Additionally, we hypothesize that the regimen under study will be better tolerated.

The benefit seen in PACIFIC, along with the growing role of immunotherapy for the treatment advanced (stage IV) NSCLC, suggests that earlier exposure to durvalumab may improve outcomes and be well tolerated, thereby permitting de-escalation of therapy through removal of conventional chemotherapy from these regimens. Indeed, the resulting improved outcomes from adding durvalumab to chemoradiation in the PACIFIC trial represent a greater magnitude of benefit from immunotherapy than was achieved from adding chemotherapy to thoracic radiation therapy. EORTC08844 compared radiotherapy alone, concurrent radiotherapy plus weekly low dose cisplatin and concurrent radiotherapy plus daily cisplatin (Schaake-Koning et al., 1992) showed improved overall survival rate of 12% with radiotherapy alone, 19% with weekly cisplatin and 26% with daily cisplatin. Another study showed similar improvement with the addition of carboplatin and VP16 (Jeremic, Shibamoto, Acimovic, & Djuric, 1995). They also represent a greater degree of benefit than has been observed from the addition of immunotherapy to chemotherapy in advanced NSCLC. Recently, IMpower131 trial enrolled 1,021 patients with stage IV squamous NSCLC randomly assigned to either atezolizumab plus carboplatin and nab-paclitaxel or carboplatin and paclitaxel alone. The median progression free survival is 6.3 months for atezolizumab plus chemotherapy compared to 5.6 months for chemotherapy alone (P=0.001) (Robert M. Jotte, 2018). Together, these observations suggest that thoracic radiation therapy and durvalumab represent a particularly favorable combination, supporting years of preclinical studies and case reports demonstrating synergy between radiation therapy and immunotherapy. PACIFIC2 and other ongoing trials provide evidence that concurrent thoracic radiation therapy and immune checkpoint inhibitor therapy is likely to be well tolerated. For example, concurrent palliative radiotherapy with durvalumab was well-tolerated in a cohort of patients included in a phase ½ trial in France (Levy, Massard, Soria, & Deutsch, 2016).

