# 2.2 Secondary Objectives

- 2.2.1 To assess the safety and tolerability of concurrent durvalumab and radiotherapy compared to historical data from patients treated with standard of care chemoradiation;
- 2.2.2 To determine the overall survival (OS) defined as the time from study enrollment to death due to any cause;
- 2.2.3 To determine the distant metastases-free survival defined as the time from the study enrollment to any new distant lesion;
- 2.2.4 To determine the local and regional control defined as the time from the study enrollment to any local and regional lesion;

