### 2.4 Endpoints

- 2.4.1 Primary endpoint of 12-month progression-free survival (PFS) rate is based on an assessment by an investigators according to RECIST 1.1 criteria; PFS is defined as the time from the study enrollment to documented progressive disease or death due to any cause, whichever occurs first;
- 2.4.2 Secondary endpoint of safety and tolerability will be assessed by adverse event according to CTCAE V.5;
- 2.4.3 Secondary endpoint of overall survival is defined as the time from study enrollment to death due to any cause;
- 2.4.4 Secondary endpoint of distant metastases free survival is defined as the time from the study enrollment to any new distant lesion;
- 2.4.5 Secondary endpoint of local and regional control defined as the time from the study enrollment to any local and regional lesion;
- 2.4.6 Exploratory endpoint of biomarker and biomarker correlatives;
- 2.4.7 Exploratory endpoint of proportion of patients alive at 12 and 24 months.

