#### 7.1.3 Adverse Reactions

In patients with Stage III NSCLC in the PACIFIC study (IMFINZI n=475), the most common adverse reactions (≥20% of patients) were cough (40%), fatigue (34%), pneumonitis or radiation pneumonitis (34%), upper respiratory tract infections (26%), dyspnea (25%), and rash (23%). The most common Grade 3 or 4 adverse reaction (≥3%) was pneumonia (7%).

In patients with Stage III NSCLC in the PACIFIC study (IMFINZI n=475), discontinuation due to adverse reactions occurred in 15% of patients in the IMFINZI arm. Serious adverse reactions occurred in 29% of patients receiving IMFINZI. The most frequent serious adverse reactions (≥2% of patients) were pneumonitis or radiation pneumonitis (7%) and pneumonia (6%). Fatal pneumonitis or radiation pneumonitis and fatal pneumonia occurred in <2% of patients and were similar across arms.

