#### Acute Adverse Events

Adverse events occurring in the time period from the signing of the informed consent, through 90 days post treatment will be considered acute adverse events.

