#### 10.3.2 Toxicities:

Only adverse events assessed to be definitely, probably, or possibly related to protocol treatment will be considered. Toxicity rate and it confidence interval will be estimated using an exact binomial approach.

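### A single related-event toxicity rate with no phase, window or grade cannot give the like-for-like comparison with chemoradiation that objective 2.2.1 asks for

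*Combined protocol and SAP*

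**What the plan says.** Section 10.3.2 (Toxicities) consists of two sentences. The first restricts the events: "Only adverse events assessed to be definitely, probably, or possibly related to protocol treatment will be considered". The second names the analysis: "Toxicity rate and it confidence interval will be estimated using an exact binomial approach". Section 6.2 makes the population everyone who received at least one dose. The endpoint in 2.4.2 adds only the grading scale: "Secondary endpoint of safety and tolerability will be assessed by adverse event according to CTCAE V.5". None of these gives a grade threshold, a window, a treatment phase or a historical rate.

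The safety objective, 2.2.1, is comparative: "To assess the safety and tolerability of concurrent durvalumab and radiotherapy compared to historical data from patients treated with standard of care chemoradiation". The rationale (1.4) asks whether giving durvalumab during and after radiation "provides comparable outcomes to concurrent chemoradiation followed by consolidation durvalumab", and adds: "Additionally, we hypothesize that the regimen under study will be better tolerated". The Study Summary lists concurrent chemoradiation alone as reference therapy. Section 1.1 describes durvalumab consolidation after chemoradiation as the current standard.

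In 7.2.1, events from consent "through 90 days post treatment will be considered acute adverse events", and later events are late, up to 5 years. The section does not say which treatment the 90 days follow.

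**The concern.** The safety question is a comparison, and a comparison needs the same window, event definition and regimen on both sides. The most natural default under 10.3.2 is to count every related event in every dosed patient. That puts radiotherapy and up to a year of durvalumab into one proportion. Set against chemoradiation alone, the trial side would carry months of consolidation toxicity that the historical side does not have. Set against chemoradiation followed by durvalumab, a whole-course rate would be suitable, but 2.2.1 does not name that comparator.

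Because phase, window, grade and comparator are all open, each could be chosen after the data are seen. Better tolerability is the rationale's stated hypothesis alongside comparable outcomes, so a loosely defined rate weakens one of the trial's main messages.

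**Working it through.** **1. The plan's own figure.** The plan states no toxicity rate, margin or interval width. The only relevant number is the sample size in 10.2: 47/0.95 = 49.5, rounded up to 50. That is the denominator if every enrolled patient is dosed.

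**2. Windows compatible with 10.3.2.** Inputs: 30 fractions (Study Summary), taken as 6 weeks or 42 days; durvalumab for up to one year (4.1.1); 90 days (7.2.1).

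- Radiotherapy phase: 6 weeks.
- Radiotherapy plus 90 days: (42 + 90)/7 = 18.9 weeks.
- Whole course plus 90 days: 52 + 90/7 = 64.9 weeks if the year includes radiotherapy, or 6 + 52 + 90/7 = 70.9 weeks if it follows radiotherapy.
- Including late events: to 5 years after treatment (7.2.1).

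**3. What 2.2.1 covers.** The primary objective, 2.1.1, names both the concurrent and the consolidative phase. Objective 2.2.1 names only the concurrent part. The imaging footnotes in 5.4 use the same concurrent expression for the radiotherapy phase alone. The wording therefore points to that phase, though it does not settle the matter.

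**4. Benchmarks in the documents.** Table 1 comes from patients randomised after chemoradiation (1.2). Section 10.2 adds that they had already tolerated it without progressing. By inference, neither arm of Table 1 contains chemoradiation-phase events. Sections 1.2, 1.3 and 7.1.3 hold other safety figures, but none is a chemoradiation-phase rate.

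**5. How far the window can move the rate (illustration).** Let c be the concurrent-phase rate and l the later-phase rate. If the phases are independent, the whole-course rate is W = 1 − (1 − c)(1 − l). The values of c (10%, 20%, 30%) are assumed. The values of l run from an assumed 10% to 142/475 = 29.9%, the grade 3 or 4 figure for any event in Table 1's durvalumab arm.

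| c | l = 10% | l = 20% | l = 29.9% |
|---|---|---|---|
| 10% | 19.0% | 28.0% | 36.9% |
| 20% | 28.0% | 36.0% | 43.9% |
| 30% | 37.0% | 44.0% | 50.9% |

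For example, 1 − 0.8 × 0.701 = 0.439. On 50 patients, a concurrent-phase 10/50 = 20% has an exact 95% interval of 10.0% to 33.7%. The whole-course 22/50 = 44% has an interval of 30.0% to 58.7%.

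**6. Dependence between phases.** Without independence, W lies between the larger of c and l (complete overlap) and c + l (no overlap). For c = 20% and l = 29.9% that is 29.9% to 49.9%. If overlap is complete and l is no larger than c, the whole-course rate equals the concurrent rate.

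**The case against.** The strongest reply is that 10.3.2 does not say what a critic might infer from it.

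- **The window.** A reader might infer that the plan fixes radiotherapy plus a year plus 90 days. It does not. The 90 days belong to the acute label in 7.2.1, which 10.3.2 never invokes, and collection continues to 5 years. The window is undefined, not wrongly defined. This stands.
- **The judgement.** A reader might infer that tolerability will be judged on unlike windows. Section 10 plans estimation only, with no benchmark, margin or rule, and better tolerability is a hypothesis in 1.4. This also stands: the comparison promised in 2.2.1 is missing rather than done wrongly.
- **The 29.9%.** It is not shown to be limited to related events, and the placebo arm shows 26.1% in the same row. It can serve only as an upper input.
- **Two PACIFIC rate sets.** Rash is 12.2% in Table 1 and 23% in 7.1.3. Grade 3 or 4 pneumonia is 4.4% in Table 1, while 7.1.3 calls it "The most common Grade 3 or 4 adverse reaction" at 7%. It is tempting to say the safety conclusion turns on which set is picked. The documents do not support that: both are background, neither is named as a benchmark, neither is chemoradiation alone, and pneumonitis agrees (33.9% and 34%).
- **Shorthand.** Objective 2.2.1 may mean the whole regimen. If so, a mismatch remains, because up to a year of durvalumab would then be set against chemoradiation alone.

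It can also be said that 5.4 schedules adverse event evaluation separately by phase, so a split remains possible. That is true, and it is why the fix is cheap, but the plan does not commit to it.

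**Conclusion.** The narrower point holds. The plan has one undivided rate of related events with no grade, window or phase. Its safety objective names a comparison that section 10 does not specify, and the comparator differs between the Study Summary and 2.2.1 on one side and 1.1 and 1.4 on the other. A whole-course rate would not answer 2.2.1 like for like.

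The size cannot be established from the documents. Under independence and the assumed inputs, concurrent-phase rates of 10% to 30% become whole-course rates of 19% to 51%. This shows that the choice of window can matter; it does not predict this trial's rates. The point concerns a secondary objective and leaves the primary analysis untouched, but it should be settled before the safety data are analysed.

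**What to change.** In 10.3.2, state the grade threshold and report two rates with exact binomial intervals:

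1. First treatment to 90 days after the last radiotherapy fraction, for comparison with a chemoradiation benchmark named before analysis and matched on window, grade and attribution rule. This window includes early consolidation durvalumab, which the report should say.
2. Whole course, for comparison with chemoradiation followed by durvalumab.

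Any comparison with Table 1 should count from the end of radiotherapy, because those patients were randomised after chemoradiation. Starting it 90 days later would drop the early weeks after radiotherapy, when section 4.4.12 expects pneumonitis and which Table 1 can include. The report should also note that Table 1 is not shown to be limited to related events.

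Reconcile the comparator across the Study Summary, 1.1, 1.4 and 2.2.1. In 7.2.1, say which treatment the 90 days follow, and anchor the acute/late split for radiation effects on the last fraction. At present 7.3.2 counts its 90-day reporting period from the last durvalumab dose, while 4.6 counts follow-up from concurrent durvalumab/radiotherapy.

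Cost: wording changes and some extra tabulation. Adverse events are already evaluated weekly during radiotherapy, at each consolidation infusion and at follow-up visits (5.4), so the split needs only event dates and the last-fraction date. The chemoradiation-phase rate is the real cost, since it must be sourced from outside the documents.

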#### 10.3.3 Exploratory Endpoints:

Exploratory data analysis will be conducted for the exploratory endpoints. Generalized estimating equation (GEE) approach will be used to investigate if there are significant changes in biomarkers over time. Proportion of patients alive at 12 and 24 months will be estimated using the Kaplan-Meier method.

#### 10.3.4 Interim Reports to Monitor the Study Progress

Interim reports with descriptive statistics will be prepared twice a year until the initial manuscript reporting the treatment results has been accepted for publication. In general, the interim reports will contain information about the patient accrual rate with a projected completion date for the accrual phase; data quality; compliance rate of treatment delivery with the distributions of important prognostic baseline variables; and the frequencies and severity of adverse events.

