In addition to trials in advanced disease, durvalumab was investigated in stage III non-resectable NSCLC in the PACIFIC trial. In this study, patients were randomized to durvalumab 1500 mg IV or placebo every 14 days for up to one year, following completion of concurrent chemoradiation. The durvalumab arm demonstrated improved PFS and OS compared to the placebo arm (Figure 1). Tumor PD-L1 expression was tested retrospectively using archival tumor tissue obtained prior to chemoradiotherapy. Durvalumab improved overall survival for all but PD-L1 <1% group (Figure 2A). Durvalumab also improved progression-free survival in each of the PD-L1 subgroups (Figure **2 B).** Limitations of PD-L1 subgroup analyses include the post-hoc nature with no pre-specified statistical adjustmetn, incomplete sample collection and small sample size of subgroups, the low number of events resulting in imbalances in baseline clinical characterisitics. The most common treatment-related adverse events included cough, pneumonitis, dyspnea, fatique and diarrhea. Apparent immune-related adverse events included pneumonitis, pruritis and rash. Table 1 lists AEs by treatment arm and severity. Pneumonitis, arguably the greatest concern in a trial combining sequential thoracic chemoradiation and immune checkpoint inhibition, was numerically increased in the durvalumab arm, but severe cases remained less than 5%: 33.9 (3.4% grade 3-4) in the durvalumab arm versus 24.8% (2.6% grade 3-4) in the placebo arm. Toxicity event terms that could represent similar processes, such as dyspnea and pneumonia, occurred at comparable rates between durvalumab and placebo arms, and reached grade 3-4 in fewer than 5% of patients. The use of combination therapies may contribute to the increased incidnece of penumonitis in the PACIFIC trial compared to the previously reported 3-5% (Suresh et al., 2018). Additionally, most cases of pneumonitis were reversible with stopping treatment, initiating glucocorticoids, or both.

Figure 1. Overall Survival (A) and Progression Free Survival (B) in PACIFIC study (A)

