# **Pulmonary Toxicity**

Pneumonitis is possible in the later weeks of chemoradiotherapy and during the weeks that follow. In general, pneumonitis is a diagnosis of exclusion and is treated with a combination of corticosteroids and supportive care at the discretion of the treating physician.

Radiographic evidence of radiation change and subsequent fibrosis of the lung will occur within lung volume receiving ≥ 20 Gy, usually within the first 6 months after initiation of treatment. It is essential to spare as much normal lung as possible in order to avoid symptomatic lung injury.

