# 7.3.1 Reporting SAEs and UPIRSOs to the Simmons Comprehensive Cancer Center (SCCC) Data Safety Monitoring Committee (DSMC)

All SAE/UPIRSOs at all sites, which occur in research subjects on protocols for which the SCCC is the DSMC of record require reporting to the DSMC regardless of whether IRB reporting is required. All SAEs/UPIRSOs occurring during the protocol-specified monitoring period should be submitted to the SCCC DSMC within 5 business days of the PI or delegated study team members awareness of the event(s). In addition, for participating centers other than UTSW, local IRB guidance should be followed for local reporting of serious adverse events.

The UTSW Radiation Oncology research office is responsible for submitting SAEs/UPIRSOs to the SCCC DSMC Coordinator and AstraZeneca. Hardcopies or electronic versions of the eIRB Reportable Event report; FDA Form #3500A forms, or other sponsor forms, if applicable; and/or any other supporting documentation available should be submitted to the DSMC Coordinator. The DSMC Coordinator forwards the information onto the DSMC Chairman who determines if immediate action is required. Follow-up eIRB reports, and all subsequent SAE/UPIRSO documentation that is available are also submitted to the DSMC Chair who determines if further action is required.

Written reports to:

Department of Radiation Oncology Clinical Research Office The University of Texas Southwestern Medical Center

[contact]

UTSW SCCC Data Safety Monitoring Committee Coordinator

Email: [contact] [contact] or deliver to BLB.306

UTSW Institutional Review Board (IRB)

Submit a Reportable Event via eIRB with a copy of the final sponsor report as attached supporting documentation

Reporting Unanticipated Problems Involving Risks to Subjects or Others (UPIRSOs) to the UTSW HRPP/IRB

UTSW reportable event guidance applies to all research conducted by or on behalf of UT Southwestern, its affiliates, and investigators, sites, or institutions relying on the UT Southwestern IRB. Additional reporting requirements apply for research relying on a non-UT Southwestern IRB.

According to UTSW HRPP/IRB policy, UPIRSOs are incidents, experiences, outcomes, etc. that meet ALL three (3) of the following criteria:

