- 1. Unexpected in nature, frequency, or severity (i.e., generally not expected in a subject's underlying condition or not expected as a risk of the study; therefore, not included in the investigator's brochure, protocol, or informed consent document),AND
- 2. Probably or definitely related to participation in the research, AND
- Suggests that the research places subjects or others at a greater risk of harm (including physical, psychological, economic, or social harm) than was previously known or recognized. Note: According to OHRP, if the adverse event is serious, it would always suggest a greater risk of harm.

For purposes of this policy, UPIRSOs include unanticipated adverse device effects (UADEs) and death or serious injury related to a humanitarian use device (HUD).

UPIRSOs must be promptly reported to the UTSW IRB within 5 working days of PI awareness.

For research relying on a non-UT Southwestern IRB (external, central, or single IRB):

Investigators relying on an external IRB who are conducting research on behalf of UT Southwestern or its affiliates are responsible for submitting **LOCAL** UPIRSOs to the UT Southwestern IRB within 5 working days of PI awareness. Investigators must report to their relying IRB according to the relying IRB's policy. In addition, the external IRB's responses or determinations on these local events must be submitted to the UT Southwestern IRB within 10 working days of receipt.

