#### 11.4 Data Management and Monitoring/Auditing

REDCap is the UTSW SCCC institutional choice for the electronic data capture of case report forms for SCCC Investigator Initiated Trials. REDCap will be used for electronic case report forms in accordance with Simmons Comprehensive Cancer Center requirements, as appropriate for the project

The Medical Oncologist investigators and delegates, will perform an Immunotherapy Assurance Review of all patients in this trial. The Radiation Oncologist investigators and delegates, will perform an RT Quality Assurance Review after the first 20 cases enrolled. Subsequent reviews will continue in a periodic and timely fashion. The final cases will be reviewed within 3 months after this study has reached the target accrual. The goal of the review is to evaluate protocol compliance. The scoring mechanism is: Per Protocol, Variation Acceptable, and Deviation Unacceptable.

The UTSW Simmons Comprehensive Cancer Center (SCCC) Data Safety Monitoring Committee (DSMC) is responsible for monitoring data quality and patient safety for all UTSW SCCC clinical trials. As part of that responsibility, the DSMC reviews all local serious adverse events and UPIRSOs in real time as they are reported and reviews adverse events on a quarterly basis. The quality assurance activity for the Clinical Research Office provides for periodic auditing of clinical research documents to ensure data integrity and regulatory compliance. A copy of the DSMC plan is available upon request.

The SCCC DSMC meets quarterly and conducts annual comprehensive reviews of ongoing clinical trials, for which it serves as the DSMC of record. The QAC works as part of the DSMC to conduct regular audits based on the level of risk. Audit findings are reviewed at the next available DSMC meeting. In this way, frequency of DSMC monitoring is dependent upon the level of risk. Risk level is determined by the DSMC Chairman and a number of factors such as the phase of the study; the type of investigational agent, device or intervention being studied; and monitoring required to ensure the safety of study subjects based on the associated risks of the study. Protocol-specific DSMC plans must be consistent with these principles.

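### No toxicity count or rate that would pause accrual is printed for durvalumab given with 60 Gy thoracic radiotherapy; the decision rests on committee judgement without a stated limit

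*Combined protocol and SAP*

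**What the plan says.** The statistical section treats toxicity descriptively. Section 10.3.4 states that "Interim reports with descriptive statistics will be prepared twice a year", covering accrual, data quality, treatment compliance, and adverse event frequency and severity. Section 10.3.2 estimates a treatment-related toxicity rate with an exact binomial interval and names no tolerable rate. The sample size in section 10.2 rests on progression-free survival alone.

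Oversight sits elsewhere. Under section 7.3.1 every serious adverse event (SAE) and every unanticipated problem (UPIRSO) goes to the DSMC within 5 business days, and "The DSMC Coordinator forwards the information onto the DSMC Chairman who determines if immediate action is required". Under section 11.4 the DSMC "reviews all local serious adverse events and UPIRSOs in real time as they are reported and reviews adverse events on a quarterly basis". One of the conditions for a UPIRSO in section 7.3.1 is that the event be "Unexpected in nature, frequency, or severity". Section 11.4 also says that a DSMC plan can be obtained on request and that "Protocol-specific DSMC plans must be consistent with these principles".

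Two other places come close to a rule. Section 4.8 treats 7 or more doses missed for toxicity as dose-limiting, but uses this only to bar replacement of the patient. Appendix I gives hold and discontinue rules for individual patients.

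**The concern.** The regimen gives durvalumab during thoracic radiotherapy. Section 1.2 describes "Pneumonitis, arguably the greatest concern in a trial combining sequential thoracic chemoradiation and immune checkpoint inhibition", and here the two treatments overlap. The protocol's stage III pneumonitis rates come from the PACIFIC trial, where durvalumab started after chemoradiation was complete. Section 10.2 itself notes that those patients had come through chemoradiation and so were selected. The concurrent experience cited in section 1.4 as an example is palliative radiotherapy in a cohort of a phase 1/2 trial.

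This weakens the frequency condition for a UPIRSO. An event can be unexpected in frequency only against an expected frequency, and the protocol gives none for durvalumab with 60 Gy. In a single-arm open-label trial each pneumonitis case can also be put down to radiation, infection or drug. Cases judged one at a time may each look explicable while the aggregate rate is unacceptable. What is at stake is patient safety. The inference on progression-free survival is not affected.

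**Working it through.** **The plan's own figure.** There is no toxicity figure to reproduce. The planned number does reproduce, from progression-free survival alone. For a one-sample log-rank test, N = (z₀.₉₀√p0 + z₀.₈₀√p1)² / (p0 − p1)², with:

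- p1 = 0.7443, the event probability at hazard 0.5978 with 3 years' accrual and 1 year's follow-up;
- p0 = 1.4 × 0.7443 = 1.0420, the expected event count per patient under the margin hazard;
- one-sided alpha 0.10.

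This gives (1.2816 × 1.0208 + 0.8416 × 0.8627)² / 0.2977² = 46.7, so 47. Then 47/0.95 = 49.5, so 50. No toxicity quantity enters.

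**Benchmarks in the protocol, all after completed chemoradiation.** Grade 3-4 pneumonitis is 16/475 = 3.4% (Table 1), and serious pneumonitis is 7% (section 7.1.3). In 50 patients that means 0.034 × 50 = 1.7 and 0.07 × 50 = 3.5 cases.

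**Pace.** 50/36 = 1.39 patients a month, one every 0.72 month, about 4 per quarterly review. Even accrual is assumed.

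**Illustrative boundary.** Assume a 10% limit, pneumonitis only, with a look every 4 patients. Pause at the smallest k for which P(p > 0.10 | Beta(0.2 + k, 1.8 + n − k)) > 0.95. This gives 3/8, 4/12, 5/16, 5/20, 6/24, 7/28, 7/32, 8/36, 8/40, 9/44 and 9/48.

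**Results.** The column with events known at once is an exact recursion. The other columns come from 100,000 simulated trials each, counting at a look only events that have already appeared. Radiographic lung change is described in section 4.4.12 as occurring "usually within the first 6 months after initiation of treatment", which makes onset over 0-6 months a reasonable central case. The longest window is 12 months of treatment plus 90 days, about 15 months. Entries are chance of pause; mean treated; eventual cases among those treated, including cases that appear after the pause.

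| Assumed true rate | Cases if all 50 accrue | Known at once | Onset uniform over 0-6 months | Onset at 6 months | Onset uniform over 15 months |
|---|---|---|---|---|---|
| 20% | 10 | 72%; 30; 6.0 | 56-57%; 39; 7.7 | 41%; 44; 8.8 | 35%; 46; 9.1 |
| 25% | 12.5 | 91%; 22; 5.5 | 82%; 31; 7.8 | 69%; 39; 9.7 | 63%; 41; 10.2 |
| 30% | 15 | 98%; 16; 4.9 | 95%; 25; 7.6 | 88%; 33; 10.0 | 84%; 36; 10.7 |

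At a true 15% the chances of a pause are 39, 25, 14 and 11% across the four settings, with about 40, 45, 48 and 49 treated.

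**Unnecessary pauses**, highest when events are known at once: 0.2% at a true 3.4%, 0.9% at 5%, 3.0% at 7%, 7.4% at 9% and 10.9% at 10%. At 7% this falls to 0.9% with onset over 0-6 months and to 0.3% with onset at 6 months.

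**Another schedule.** Looks after 10, 20, 30 and 40 patients with an exact one-sided 5% rule at 10% give cut-offs of 4, 5, 7 and 8. The chance of a pause is 7.3% at 10% and 85% at 25%, with about 26 treated at 25%. The gain does not depend on one choice of boundary.

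**Adding treatment-related deaths.** With an assumed 1-2% of other such deaths, 20% becomes 1 − 0.80 × 0.99 = 20.8% or 1 − 0.80 × 0.98 = 21.6%, and 7% becomes 7.9% or 8.9%.

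**The case against.** Existing oversight is substantial. Appendix I requires hospitalisation and permanent discontinuation for grade 3-4 pneumonitis. Such a case would normally be an SAE and would reach the DSMC individually, sooner than a quarterly look. Eligibility limits on lung function and interstitial lung disease, together with the lung dose constraints, also reduce risk. Section 10.3.4 describes progress reports and is not the main safety mechanism. The DSMC plan is not among the documents and could hold a trigger.

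The arithmetic can be challenged too. The comparison with 50 accrued patients supposes a committee that never acts, so the gain over existing SAE review is not measured. The 10% limit and the 20-30% rates are assumptions. At 15%, above the limit, the boundary usually does not pause. With late onset at 20% it saves about one case (8.8 or 9.1 against 10). The calculation covers pneumonitis alone, and the 3.4% benchmark is grade 3-4, while the proposed event is grade 3 or higher plus treatment-related death.

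All of this stands as a limit on the size of the benefit. It does not supply the missing number: none of the mechanisms states an aggregate rate at which to act. What can be said about the DSMC plan is only that no trigger is printed or cited in the protocol.

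**Conclusion.** The concern holds. Neither phase has a printed trial-level toxicity boundary, and the protocol offers no reference rate for the concurrent combination against which the DSMC could judge an excess. As a safety-monitoring gap this should be corrected; the sample size and error rates for progression-free survival are untouched. With the illustrative boundary and an assumed true rate of 25%, expected cases fall from 12.5 to 7.8 in the central onset setting, and some reduction remains in every setting tried. These sizes rest on the assumed 10% limit, the assumed true rates, even accrual, the onset patterns, and a comparison in which all 50 patients would otherwise be treated. A trigger in a DSMC plan that was not available for review cannot be excluded.

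**What to change.** Add to sections 10.3.4 and 11.4 an accrual-pause boundary applied by the existing DSMC at its quarterly adverse event review.

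- **Event:** grade 3 or higher pneumonitis of any attribution, radiation and immune pooled as in Table 1, plus any treatment-related death. Each patient counts once, from first study treatment through 90 days after the last dose.
- **Limit:** an acceptable rate set by the investigators and the DSMC. The 10% used here is only an illustration.
- **Print in section 10:** the boundary and its operating characteristics, computed for the full composite event, with onset delay, and including rates only moderately above the limit.
- **Action:** crossing the boundary pauses new enrolment pending DSMC review. Real-time SAE review continues unchanged.

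If a DSMC plan for this trial already contains such a trigger, cite it instead.

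The cost is one paragraph and one table, with no extra patients or data. The downside is an occasional unnecessary pause: under 1% of trials at a true rate of 5% or less, up to 3.0% at 7%, and 10.9% at 10% with the illustrative boundary. Because detection weakens with late onset, the boundary supplements SAE review and does not replace it.
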